## **Study Objective**

As such, we conducted a randomized controlled trial of 105 SSPs throughout the US to understand the effectiveness of a multifaceted, external facilitation-based implementation strategy at advancing OEND implementation effectiveness within SSPs.

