#### Trial Outcomes

Our primary outcomes center on the multidimensional variable of implementation effectiveness (i.e., the consistency and quality of OEND implementation by SSP staff). Implementation effectiveness fit our broad objectives, by focusing on the extent to which our multifaceted, facilitation-based approach impacted OEND delivery at the organizational level. Accordingly, SSPs represent the primary unit of analysis. Proctor et al.'s taxonomy of implementation outcomes informs our operationalization of implementation effectiveness, focusing on the reach of SSPs' naloxone distribution (i.e., consistency) and fidelity to OEND best practices (i.e., quality)[46]. As such, the primary outcomes were the number of naloxone doses distributed in the past 3 months; the number of SSP participants receiving naloxone in the past 3 months, and the number of OEND best practices implemented. Importantly, prior research has shown that larger scale naloxone distribution has led to reductions in opioid overdose mortality, further supporting use of these measures as trial outcomes [17, 47, 48].

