#### Statistical Analysis Plan

Statistical analyses were conducted using an intent-to-treat approach. Descriptive statistics were used to summarize continuous outcomes and covariates by experimental condition; frequencies and percentages were used to summarize categorical measures. Given the varying sizes of SSPs, counts of naloxone doses and individuals receiving naloxone were summarized as a rate per number of participant contacts for syringe services in the past 3 months.

Negative binomial regression models were used to compare the number of naloxone doses distributed and contacts for naloxone refills or trainings by condition; the number of contacts for syringe services in the past 3 months was included as an offset. The model for naloxone doses was adjusted for baseline rate given the difference between conditions at baseline. The mean number of best practices adopted were compared by condition using a two-sample t-test. We also carried out a per-protocol dose response analyses, where OMIE SSPs were dichotomized at the median for the number of OMIE sessions (<10 sessions; 10+ sessions) and number of OMIE hours received (<12 hours; 12+ hours) and compared to Control SSPs. P-values <0.05 were considered statistically significant a priori. All analyses were conducted using Stata 16.1 (StataCorp LLC, Texas USA).

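### Three unranked primary outcomes serve one objective with no joint success rule; if any one sufficed, the false-positive chance favouring OMIE would be about 4–7% against 2.5%, and the second declared primary is summarised but not the variable tested

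*Combined protocol and SAP*

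**What the plan says.** The Study Objective poses one question, the effectiveness of a facilitation-based "implementation strategy at advancing OEND implementation effectiveness within SSPs". Trial Outcomes turns that construct into several measures: "Our primary outcomes center on the multidimensional variable of implementation effectiveness". It then lists three without ranking them. In the first place, "the primary outcomes were the number of naloxone doses distributed in the past 3 months"; the second is "the number of SSP participants receiving naloxone in the past 3 months"; the third is a count of OEND best practices in use.

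The Statistical Analysis Plan gives each comparison its own test. Two negative binomial models with an offset cover the counts, and for the third outcome: "The mean number of best practices adopted were compared by condition using a two-sample t-test". The only decision threshold is "P-values <0.05 were considered statistically significant a priori". Sidedness is not stated. No section gives a composite, a hierarchy, a multiplicity adjustment, or a rule on whether one, some or all outcomes must be significant. Targeted Sample Size uses one alpha of 0.05 and does not say which outcome it covers.

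On the second primary, the same SAP section says that counts of "individuals receiving naloxone were summarized as a rate per number of participant contacts", but the model it describes compares "contacts for naloxone refills or trainings by condition".

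**The concern.** Three tests at 0.05 are not a fault in themselves. The difficulty is that the objective and the outcomes section tie the three to one construct and one question, while the plan does not say how three p-values answer it. One significant result out of three could be reported as OMIE advancing implementation effectiveness, and nothing in the plan rules that out. The missing rule therefore determines the error rate of the headline claim, and a mixed result has no pre-stated meaning.

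The family is also not fully defined. One participant can make several contacts for refills or training, so a count of contacts and a count of people are different variables as worded. Taken literally, the declared second primary is described but never tested.

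**Working it through.** **Inputs from the plan.** Three primary outcomes (Trial Outcomes); threshold 0.05 per test (Statistical Analysis Plan); 50 SSPs per arm, d = 0.45, SD 1.0, two measurements, within-SSP correlation 0.3, power 80% (Targeted Sample Size).

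**Inputs assumed.** Between-outcome correlations from 0 to 0.9, since the documents give none. Two-sided tests, hence 2.5% in OMIE's favour for a single test. d = 0.45 for all three outcomes, counts included, because the plan gives power only in d units.

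**1. The plan's own power.** The mean of two measurements has variance (1 + 0.3)/2 = 0.65. The noncentrality is 0.45/√(0.65 × 2/50) = 2.79, and two-sided power is 79.7% (78.9% with the t distribution on 98 df). This reproduces the stated 80%. The one-sided version gives 87.4%, so the figure supports two-sided testing.

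**2. At least one false positive, all three nulls true.** With independent outcomes:
- favouring OMIE: 1 − 0.975³ = 0.0731
- either direction: 1 − 0.95³ = 0.1426

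For a common correlation ρ, favouring OMIE: 1 − ∫ φ(x) [Φ((1.96 − √ρ·x)/√(1−ρ))]³ dx, with the matching two-sided form for either direction.

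| ρ | Favouring OMIE (single test 2.5%) | Either direction (single test 5%) |
|---|---|---|
| 0 | 7.3% | 14.3% |
| 0.3 | 6.8% | 13.6% |
| 0.5 | 6.3% | 12.5% |
| 0.7 | 5.5% | 10.9% |
| 0.9 | 4.2% | 8.4% |

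If the two naloxone outcomes correlate 0.8 and the other pairs 0.2, simulation gives 6.1% and 12.3%.

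**3. Other rules, same nulls (simulation).** If all three must be significant, the chance is at most 2.3% over these correlations. With Holm it is 4.9% (ρ = 0) to 3.0% (ρ = 0.9) in either direction, and 2.5% to 1.5% favouring OMIE.

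**4. Mixed result (one or two of three significant) when all three effects are real at d = 0.45.** This is 1 − P(all three) − P(none). A plain two-sample t-test has noncentrality 0.45 × √(50/2) = 2.25 and power 60.6% on the t basis (61.4% normal). With independent outcomes and the sample-size model: 1 − 0.789³ − 0.211³ = 0.499.

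| ρ | Sample-size model | Plain t-test |
|---|---|---|
| 0 | 49.9% | 71.7% |
| 0.3 | 41.8% | 58.3% |
| 0.5 | 35.4% | 48.5% |
| 0.7 | 27.6% | 37.5% |
| 0.9 | 16.8% | 22.5% |

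These are t-based simulations; the normal approximation is up to about two percentage points lower.

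**5. Power per outcome under Holm (normal basis).**
- Plain t-test: 51.2% (ρ = 0) to 50.3% (ρ = 0.9) with all effects real, against 61.4% unadjusted; 44.4% if only one is real. The t basis is about one point lower.
- Sample-size model: 74.7% to 71.2%, against 79.7%.

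**The case against.** The strongest reply is that the inflation belongs to a reading the plan never adopts. The construct is called multidimensional, its dimensions are assigned to different measures, and each outcome has its own comparison. That fits claims made outcome by outcome, where each keeps 5%. Adjusting separately declared primary outcomes is also partly a matter of preference, and no error target in the documents calls for Holm. This stands: a reader might infer that the plan runs at a 14% error rate, or that the sponsor intended any one outcome to suffice, and the documents support neither. They are silent on the rule.

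A reader might also infer that a mixed result is likely even if OMIE works. The figures do not support that across their range. On the sample-size model they never exceed one half, and on the plain t-test they do so only at correlations 0 and 0.3.

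The power figures near 80% come from averaging two repeated measurements, which is not an analysis the SAP runs. The plain t-test matches only the best-practices comparison, and no calculation here matches the offset count models. Holm's cost should therefore not be judged from the sample-size model alone.

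The people-versus-contacts mismatch is a separate defect and adds nothing to the 4–7%. It may be loose wording for one variable, which the documents cannot settle. What survives all of this is that no section links the three results to the single objective.

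**Conclusion.** The point holds in a conditional form. Three unranked primary outcomes serve one objective, each is tested at an unadjusted 0.05, and no joint success rule is given. If, and only if, any one significant outcome is read as success, the false-positive chance under the global null is about 4–7% favouring OMIE against 2.5%, or 8–14% in either direction against 5%. This rests on assumed correlations of 0.9 to 0, assumed two-sided tests, and each test holding its nominal level. A mixed result with all three effects real at d = 0.45 is possible, with probability about 17% to 72% depending on the correlation and power model. The session and hour dose-response comparisons are not counted.

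Separately, as written, the declared second primary is summarised but not tested. The point is moderate: it limits what may be claimed and does not invalidate any single comparison.

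**What to change.** 1. Fit the negative binomial model, with the same offset, to participants receiving naloxone and treat it as the primary test. Label any model of contacts secondary. If the two terms mean one variable, say so.
2. Report Holm-adjusted p-values for the three primary comparisons (steps 0.05/3 = 0.0167, 0.05/2 = 0.025, 0.05) beside the unadjusted estimates and confidence intervals. Label them post hoc if they were not set before analysis.
3. State that no joint success rule was pre-specified. Describe a mixed result outcome by outcome, say which outcomes survive Holm, and do not claim an overall improvement in implementation effectiveness from one unadjusted p<0.05.

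No new data are needed. Holm uses three p-values, and the declared second primary needs at most one further model on a variable the SAP already summarises. Follow-up ended in February 2022 and the plan is written in the past tense, so a Holm display added now cannot stand in for a pre-specified rule. The statistical cost is power: at d = 0.45 with 50 per arm, a plain t-test falls from about 61% to about 50% per outcome, or about 44% if only one effect is real.
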